## Statistical Analysis Plan

In this small pilot trial of three participants, we calculated and reported descriptive statistics (means and standard deviations) with the different conditions (Habitual and Assist-Knee) to determine ranges of values for the following measures:

- Time to complete sit-to-stand
- Time to complete stand-to-sit
- Timed Up and Go Test
- Percentage of Body Weight on Contralateral Side at 65 degrees knee flexion

Due to the small sample size, the use of parametric statistical analyses such as Analysis of Variance (ANOVA) and averaging as a single group are not appropriate. Instead, each participant served as their own control since each user's prosthesis is unique, and we analyzed these values and the extremes (e.g., how fast or slow the sit-to-stand or stand-to-sit times were), to better understand the effect of our investigational device and inform sample size calculations in future research.

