Once contact is made between the prosthesis user and Orthocare Innovations' research personnel, the Orthocare Innovations phone script will be followed (Assist-Knee solicitation script.doc). The research will be thoroughly described with opportunities for asking questions. Those interested in participating and those who meet our criteria will schedule an appointment for consenting at the Orthocare Innovations Biomechanics Laboratory. At this time, we will ask if they would like the consent document mailed or emailed to them so that they will have ample time to review the document prior to their visit. If they answer yes, we will mail or email a cover letter (Assist-Knee solicitation letter.doc) with a copy of the prosthesis user's consent document (Assist-Knee consent subject.doc).

Experimental procedures

Since each participant's prosthesis is unique, the prosthesis users will act as their own controls. All participants will have at least one visit to the Orthocare Innovations Biomechanics Laboratory, with each visit expected to last a minimum of four hours. The participants will first complete a baseline data collection using their existing habitual prosthesis. The participant's individual power harvesting performance, kinematic data, and kinetic data will be measured in the Orthocare Innovations Biomechanics Laboratory for baseline comparisons, using a motion capture system (Vicon, Centennial, CO and force plates (AMTI, Watertown, MA). The participants will be asked to perform a variety of common activity tasks that may include: sit-to-stand maneuvers, walking on level-ground; turns during walking on level ground; initiating gait from a standstill; and stand-to-sit maneuvers. The main focus of the data collection is during the sit-to-stand-to-sit maneuvers. The participants will also be asked to complete the Timed Up and Go (TUG) test, which requires the participant to stand up from a chair, walk 3 m, turn around, walk 3 m back to the chair, turn around, and sit down onto the chair. After baseline data have been collected, the prosthesis user will then wear Assist-Knee and complete the same data collection in the Biomechanics Laboratory. Subjects will be asked to complete the Prosthesis Evaluation Questionnaire (PEQ) and a custom survey after completing the data collection for each habitual or Assist-Knee condition (Assist-Knee_ParticipantQuestionnaire.docx). Subjects will also be asked to complete a demographic survey (Assist-Knee_Demographics.doc).

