Participants will wear the Assist-Knee system (**Figure 4**), which is designed to fit in place of their existing knee prosthesis and ankle-foot prosthesis. {text redacted}

{figure redacted }

Figure 4: Representation of participant using Assist-Knee

An Orthocare Innovations study research prosthetist will fit each participant with the Assist-Knee device. The participant will be trained by the research prosthetist on how to use Assist-Knee with an acclimation period of at least 60 minutes, with rest periods as needed, or until the subject feels comfortable using the system independently for gait and sit-to-stand-to-sit transitions. We intend to provide ample training on the system before independent use and will provide an operator for the clinical study if necessary. We will then test the effect of Assist-Knee on various movements (sitting down, standing up, gait via TUG test) and collect kinetic, kinematic, and temporal-spatial data. The data will be collected using the Orthocare Innovations' Biomechanics Laboratory motion capture system (Vicon, Centennial, CO), force plates (AMTI, Watertown, MA), and a commercially available sensor (Smart Pyramid with Compas, Orthocare Innovations, Edmonds, WA) attached to the Assist-Knee.

To mimic current clinical practice, the Assist-Knee device will be aligned by the prosthetist in static alignment to an optimal state by consensus of the research prosthetist and participant. { text redacted } The subject will be given an acclimation period of at least 10 minutes, with rest periods as needed, or until the subject feels comfortable using the system with each new combination. When performing the activities during the entire experiment, the participant will wear a gait belt held by the clinician for safety. Kinematic and kinetic data will be recorded.

For each combination, subjects will perform a variety of tasks that may include: sit-to-stand maneuvers, walking on level-ground; turns during walking on level ground (e.g. for the TUG test); initiating gait from a standstill; and stand-to-sit maneuvers. The participants will not be allowed to use an assistive device during the sit-to-stand and stand-to-sit transitions, but the participants will be allowed to use an assistive device during the walking portion of the TUG test. The data

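### Must the SAP name the Assist-Knee minus Habitual difference and say what its SDs are taken over?

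*SAP*

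**What the plan says.** The SAP (Statistical Analysis Plan) reports "descriptive statistics (means and standard deviations) with the different conditions (Habitual and Assist-Knee") for four measures: sit-to-stand time, stand-to-sit time, the Timed Up and Go (TUG) test, and the share of body weight on the contralateral side at 65 degrees of knee flexion. It says that ANOVA and "averaging as a single group are not appropriate" with so few people, and that instead "each participant served as their own control". The values and their extremes are then examined for two purposes: to understand the device's effect and to "inform sample size calculations in future research".

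The protocol (section iii, Experimental procedures) describes the same contrast. Habitual-prosthesis data are taken in the "Biomechanics Laboratory for baseline comparisons, using a motion capture system", and the participant will then "wear Assist-Knee and complete the same data collection in the Biomechanics Laboratory". Data are collected at several Assist-Knee combinations ("For each combination, subjects will perform a variety of tasks"), whose content is redacted. At least five motion-analysis trials and three TUG trials are required for each combination. Protocol section iv lists the data and outcome measures but gives no rule for summarising them.

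**The concern.** The design is within-person, yet the SAP's text describes each condition separately. It names no difference, ratio or percentage change, and it does not say in words what the SDs are taken over. The possible meanings are not interchangeable:

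- An SD over one person's trials measures repeatability. It says nothing about how the device effect varies between people.
- An SD over the three people within a condition leaves out the correlation between a person's two conditions.
- The SD of the within-person differences is what a paired future trial would need, and it is not mentioned.

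Pilot data for a larger trial is one of the two purposes in protocol section i, and the SAP itself mentions sample size. The risk is that someone planning that trial takes a repeatability SD for the between-person SD of the effect. The SAP also has one Assist-Knee label where the protocol has several combinations, so it might seem unclear which collection a reported value comes from.

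**Working it through.** The documents give no alpha, power, effect size, SD or correlation, and the target of 3 participants has no derivation. There is therefore no plan figure to reproduce. The check has four steps.

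**1. What the SDs are most likely over.** An SD across three participants is taken around a group mean, and the SAP says that averaging the participants as one group is not appropriate. Its replacement is the participant as own control. With at least 5 motion trials and 3 TUG trials per combination, each person supplies enough repeats for a mean and an SD. Together these point to SDs over trials within a participant. No sentence says so outright, but the across-participant reading conflicts with the SAP's own text.

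**2. What is missing for the difference.** On that reading each person has a Habitual mean and an Assist-Knee mean for each measure. With one Assist-Knee value per measure, there are 4 measures x 3 participants = 12 differences, each one a subtraction. The trial noise in one person's difference also follows from the trial SD. With k independent trials per condition and a common trial SD s,

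SE = s x sqrt(2/k)

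- k = 5 (motion): sqrt(2/5) = 0.63, so SE = 0.63 s
- k = 3 (TUG): sqrt(2/3) = 0.82, so SE = 0.82 s

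This assumes that the stated minimums apply to the Habitual collection as well. It leaves out variation in the device effect between people, for which the documents give no figure.

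**3. Whether the type of SD matters in principle.** It does. Assume, outside the documents, a paired trial with two-sided alpha 0.05, power 80% and an effect delta of 0.5 between-person SDs within a condition. Then SD_diff = SD x sqrt(2(1 - rho)) and n = ((1.96 + 0.84) x SD_diff / delta)^2, rounded up:

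| rho | SD_diff / SD | n |
|---|---|---|
| 0 | 1.414 | 63 |
| 0.5 | 1.000 | 32 |
| 0.9 | 0.447 | 7 |

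By-condition SDs alone do not fix a paired sample size.

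**4. Whether adding the SD of differences would solve that.** Three differences leave 2 degrees of freedom. Assuming normal differences, the 95% limits as multiples of the estimated SD are

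- lower: sqrt(2/7.378) = 0.52
- upper: sqrt(2/0.0506) = 6.28

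Sample size scales with the square of the SD, so the limits on the implied N are 0.27 and 39.5 times the point value. The ratio is 39.5/0.271, or about 146. That is wider than the ninefold spread (63 to 7) from not knowing the correlation in step 3.

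**The case for a change.** The strongest case for a change is that likely is not the same as stated. The SAP sets a within-person design and a planning aim, and between them names only values and extremes. One sentence defining the difference and the unit of the SDs, with a table of 12 differences, would cost almost nothing and use data already collected. It would respect the refusal to average, and it could stop a later reader from using a repeatability SD as a planning SD.

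Part of this stands. The SAP does not literally name the difference or the unit, protocol section iv does not supply them, and a trial SD should not be mistaken for between-person variation in the effect.

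The rest carries less weight:

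- The planning argument presumes that the future trial is paired. Protocol section i says only that it would be a larger clinical trial in a representative population.
- The criticism of an across-participant SD is aimed at a summary that the SAP appears to rule out.
- The SAP claims only to inform later calculations, and individual values and extremes can do that.
- What the combinations are is redacted, so the single Assist-Knee label cannot be held against the plan.
- The SAP is in the past tense and the reported tables are not in the documents. The differences and labels may already be there.

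**Conclusion.** No change to the plan follows. This is a small gap in wording that an analyst fills sensibly from the SAP's own text: means and SDs over repeat trials within a person, compared between conditions within that person. The differences are 12 subtractions, or more if each combination is shown separately. The one quantity that subtraction does not give directly, an SD of the differences, rests on three people, and its roughly 146-fold range on N means it could not set a sample size on its own. There is no hypothesis test, and no result or conclusion of the pilot depends on the point.

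This rests on two assumptions: that the rejection of group averaging carries over to the SDs, and that participant-level means are available to whoever uses the data. If the tables showed only pooled values, the differences could not be recovered from them, but that would go against what the SAP says. Labelling the SDs as within-participant over trials and adding a difference column would help a reader, but this is a matter of presentation.
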